- Percent change in Fractional Excretion of Calcium (FECa) from baseline (Screening visit) to the final day of treatment (Day 6 or the last measurement while on encaleret). FECa calculated using fasting blood levels and spot urine collection.
- Change in blood iPTH comparing average baseline iPTH to average peak iPTH on encaleret. The average baseline iPTH will include all baseline iPTH levels from the screening visit, Day -1, and pre-dose on Day 1. The average peak iPTH will average the peak iPTH levels on every day the patient is on encaleret (days 1 to 5). An increase in iPTH will be considered clinically significant if there is an increase both by 50% AND by more than 10 pg/dL.
- Change in 1,25-(OH)₂ Vitamin D on encaleret comparing the maximal level prior to receiving calcitriol (On Days 3-5) to baseline (Average of Day 1 Pre-dose levels). Increase will be considered significant if there is an increase of more than 50%. Participants who receive calcitriol prior to Day 3 will be excluded.
- Pharmacodynamic endpoints measured over 5 days of encaleret therapy:

- Blood iPTH – Absolute levels and change from baseline
- Albumin-corrected blood calcium – Absolute levels and change from baseline
- Ionized Calcium – Absolute levels and change from baseline
- Urinary calcium clearance (fractional excretion and 24-hour total excretion) – Absolute levels and change from baseline
- Serum levels of 1,25-(OH)₂ Vitamin D – Absolute levels and change from baseline
- Blood intact FGF23 (iFGF23) and C-terminal FGF23 (cFGF23) – Absolute levels and change from baseline
- Urine cAMP and citrate – Absolute levels and change from baseline
- Blood bone resorption marker, collagen cross-linked C-telopeptide (CTX) – Absolute levels and change from baseline
- Blood bone formation marker, blood procollagen type 1 N-propeptide (P1NP) – Absolute levels and change from baseline
- PK parameters such as maximum plasma concentration (C_{max}), time to maximum plasma concentration (t_{max}), apparent terminal half-life (t_{1/2}).
- Change in components of urine including: supersaturation, sodium, potassium, calcium, magnesium, chloride, phosphorus, sulfate, citrate excretion, oxalate, pH, uric acid, creatinine, osmolality, ammonium, urea nitrogen, protein catabolic rate

Study Population: Enrollment up to 30 male or female participants to achieve 15 to enter the treatment phase. Two cohorts:
Cohort 1: Permanent PSH (>1 year after surgery) with minimum of 7 and up to 10 participants

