24-Hour urine: Ca, Mg, PO4, Cr, Na, K, pH, Citrate Supersaturation Panel	Days -1 to 5 0-24 hrs (Start collection after first morning void and end 24 hours later) Day -1 and Day 5

Table C: Blood Sampling Days -1 to 5

Day -1: Baseline fasting labs including CBC, acute care panel, intact PTH, Ca, PO4, Mg, Cr, albumin, K, CK, Research blood, Bone turnover markers (CTX, P1NP), 25-(OH) Vitamin D, 1,25-(OH)₂ Vitamin D, cAMP, ionized calcium, TSH, FT4

		-30 min	-15 min	30 min	1 hour	2 hour	4 hour	12 hour	16 hour	24 hour
Day 1	Mineral labs	X	X	X	X	X	X	X	X	
	Safety Labs		X					X		
	Ionized Calcium		X				X	X	X	
	Research Blood	X	X			X	X	X	X	
	Bone Turnover Markers		X							
	1,25D	X	X							
	cAMP		X							
	Pk		X			X	X			
Day 2-4	Mineral labs		X	X			X	X	X	
	Safety Labs		X					X		
	Ionized Calcium		X				X	X	X	
	Research Blood		X				X	X	X	
	Bone Turnover Markers		X							
	1,25D		X							
	cAMP		X							
	Pk		X							
Day 5	Mineral labs		X	X	X	X	X	X	X	X
	Safety Labs		X					X		
	Ionized Calcium		X				X	X	X	X
	Research Blood		X			X	X	X	X	X
	Bone Turnover Markers		X							
	1,25D		X							X
	cAMP		X							X
	Pk		X			X	X			

Mineral Labs: Intact PTH, Ca, PO4, Mg, Cr, Albumin

Safety Labs: Acute care panel (Na, K, Cl, CO₂, BUN, Cr, eGFR), CK

Research Blood

Bone turnover Markers: CTX, P1NP

1,25-(OH)₂ Vitamin D, cAMP

a

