2 INTRODUCTION

2.1 Study Rationale

This study will explore the PTH-independent effects of encaleret on calcium homeostasis in patients with low or undetectable PTH levels as a result of neck surgery (post-surgical hypoparathyroidism; PSH).

Hypoparathyroidism is characterized by an inappropriately low level of PTH which results in hypocalcemia. Inadequate PTH-secretion results in lower levels of endogenous 1,25-(OH)₂ Vitamin D (decreasing calcium absorption from the gut), lower levels of calcium reabsorption in the kidney (leading to hypercalciuria), and decreased PTH-mediated bone resorption (decreasing calcium release from the bone).

Conventional therapy with oral calcium and calcitriol, often causes hypercalciuria, which is associated with long-term morbidity including nephrolithiasis, nephrocalcinosis and chronic kidney disease (Khan et al 2018, Li et al 2018). Managing patients with hypoparathyroidism is a challenging balance between increasing blood calcium while minimizing hypercalciuria (Gafni and Collins, 2019).

To avert symptoms of hypocalcemia, patients with PSH usually require a blood calcium in the normal range. This often results in hypercalciuria and renal calcification, which in some cases leads to loss of renal function, including the need for dialysis and transplantation. As such, there is a significant unmet need in treating patients with PSH.

Encaleret is a negative allosteric modulator of the calcium-sensing receptor (CaSR), also known as a calcilytic, which decreases the sensitivity of the CaSR to calcium, resulting in decreased renal calcium excretion, and in patients with intact parathyroid glands, increased PTH secretion. Pre-clinical studies have showed that calcilytics shift the IC₅₀ of the calcium-PTH curve to the right (See IB Section 4.2.3 In Vivo Studies). In cellular and animal models of both post-surgical and genetic forms of hypoparathyroidism due to CaSR gain-of-function variants, calcilytics have been shown to shift the CaSR ‘set-point’ so as to increase renal reabsorption and PTH secretion (in animals with intact parathyroid glands), resulting in increased blood calcium (Loupy et al, 2012; Dong et al, 2015; Hannan et al, 2015).

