3 OBJECTIVES AND ENDPOINTS

OBJECTIVES	ENDPOINTS	JUSTIFICATION FOR ENDPOINTS
Primary		
Evaluate the PTH-independent effects of encaleret on renal calcium	Percent change in Fractional Excretion of Calcium (FECa) from baseline (Day -1) to the final day	FECa reflects the relationship between blood calcium and

OBJECTIVES	ENDPOINTS	JUSTIFICATION FOR ENDPOINTS
handling in participants with PSH.	of treatment (Day 6 or the last measurement while on encaleret). FECa calculated using fasting blood levels and spot urine collections.	urinary calcium. CaSR modulation by encaleret is expected to directly affect FECa. If a patient stops encaleret early prior to Day 6, the last fasting FECa on encaleret 162 mg BID will be used for this endpoint.
Secondary		
Evaluate the ability of encaleret to normalize blood calcium while maintaining a normal urinary calcium in participants with PSH.	Proportion of participants who achieve a concomitant normal or elevated fasting blood calcium (albumin-corrected calcium >8.5 mg/dL) and a normal 24-hour urinary calcium level (<250 mg/24 hours for women, <300 mg/24 hours for men) on encaleret at any point between day 1 and day 5.	Clinically relevant endpoint to determine if encaleret can allow PSH to have both normal blood and urinary calcium.
Tertiary/Exploratory		
Evaluate the ability of encaleret to increase serum iPTH levels in participants with PSH.	Change in blood iPTH comparing average baseline iPTH to average peak iPTH on encaleret. The average baseline iPTH will include all baseline iPTH levels from the screening visit, Day -1, and pre-dose on Day 1. The average peak iPTH will average the peak iPTH levels on every day the patient is on encaleret (days 1 to 5). An increase in iPTH will be	Averaging iPTH will prevent spurious excursions from impacting outcomes

OBJECTIVES	ENDPOINTS	JUSTIFICATION FOR ENDPOINTS
	considered clinically significant if there is an increase both by 50% AND by more than 10 pg/dL.	
Evaluate the effect of encaleret on 1-alpha hydroxylase action by measuring 1,25-(OH) ₂ Vitamin D levels.	Change in 1,25-(OH) ₂ Vitamin D on encaleret comparing the maximal level prior to receiving calcitriol (On Days 3-5) to baseline (Average of Day 1 Pre-dose levels). Increase will be considered significant if there is an increase of more than 50%. Participants who receive calcitriol prior to Day 3 will be excluded.	

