8.3.9 Events of Special Interest

Hypocalcemia in PSH

Hypocalcemia is not an expected side-effect of treatment with encaleret, but it is a complication of the underlying disease being treated. As such, hypocalcemia may develop whenever the underlying disease is inadequately treated and might occur due to either inadequate or missed doses of a specific, effective medication.

The current study involves reducing the dose of current maintenance medications or suspending their use entirely (i.e., oral calcium supplements and calcitriol), to facilitate evaluation of encaleret and potentially establishing clinical proof-of-principle. Under these circumstances there is a risk that participants could experience symptoms of hypocalcemia prior to reaching encaleret maximal effect. In order to mitigate this risk, the study design emphasizes safety foremost. All changes to oral maintenance medications in conjunction with encaleret dosing will be conducted with participants in residence at the Clinical Center, with multiple daily measurements of blood calcium and close supervision by health professionals with experience caring for individuals with hypoparathyroidism. In addition to these precautions, monitoring for and capture of events suggestive of or consistent with hypocalcemia will be reviewed as an AE of special interest as described below.

Adverse Events of Hypocalcemia: Symptomatic and Asymptomatic

Adverse events consistent with hypocalcemia will be classified as either symptomatic or asymptomatic, and assessed for severity, recognizing that there is a spectrum of clinical manifestations. Symptomatic hypocalcemia will be based on identification of new or worsening symptoms consistent with hypocalcemia such as numbness/tingling of hands, feet

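### The exploratory iPTH endpoint takes no account of blood calcium at the draw, so neither a rise nor a null result can be attributed to encaleret

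*Combined protocol and SAP*

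**What the plan says.** The Synopsis (1.1) and Section 3 define the endpoint as the "Change in blood iPTH comparing average baseline iPTH to average peak iPTH on encaleret". On the baseline side, "The average baseline iPTH will include all baseline iPTH levels from the screening visit, Day -1, and pre-dose on Day 1". The on-drug side is the mean of the daily peaks over Days 1-5. A rise is called clinically significant if there is an "increase both by 50% AND by more than 10 pg/dL". The only justification offered, in Section 3, is that "Averaging iPTH will prevent spurious excursions from impacting outcomes".

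On mechanism, Section 2.1 says calcilytics shift the IC50 "of the calcium-PTH curve to the right".

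On background treatment, Section 8.3.9 states: "The current study involves reducing the dose of current maintenance medications or suspending their use entirely". Table A puts the last home doses of active vitamin D and calcium on Day -2. From Day -1 a study calcium regimen and about 1000 mg/day of dietary calcium replace them (Sections 2.3.1, 6.1.2 and 8.2). Calcitriol returns on Day 3 if cCa remains below 8.5 mg/dL, or earlier as rescue. Table D leaves calcium unchanged in asymptomatic participants with cCa of 7-10.2 mg/dL.

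On measurement, Table C defines one panel: "Mineral Labs: Intact PTH, Ca, PO4, Mg, Cr, Albumin". Section 9.4.9 says only that mixed models may be used for pharmacodynamic variables. It names no calcium covariate.

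**The concern.** If the drug shifts the calcium-PTH curve, its effect is more PTH at a given calcium. A change in PTH alone mixes that shift with movement along the curve, and calcium may well move between the two sides of this comparison. The screening value is taken on conventional therapy, whereas the on-drug values come after calcitriol has been stopped and the calcium regimen changed. There is no untreated group to show what PTH does under those changes alone.

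The stated purpose of Cohort 2 (Sections 2.1 and 4.2) is to explore whether a calcilytic can raise PTH secretion in healing glands, and the matching objective concerns encaleret's ability to raise iPTH. The endpoint as defined cannot support that attribution. The plan does guard a neighbouring endpoint: the 1,25-(OH)2 vitamin D comparison uses only levels before calcitriol and excludes participants given it before Day 3. The iPTH endpoint has no comparable safeguard.

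The same iPTH values decide membership of the PTH-Clamp and Aparathyroid populations (Section 9.3). For isolating PTH-independent renal effects, sorting by actual PTH is reasonable whatever moved it. Membership should not, however, be read as showing who did or did not respond to the drug.

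**Working it through.** **Plan's own figure.** None exists for iPTH. The power figures in Section 9.2 concern FECa and have no bearing here.

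**What the documents' limits allow.** Entry cCa is 7.8-10.2 mg/dL (Section 5.1). The Table D step for cCa below 7 mg/dL is not reached at 7.0. The slope that calcium alone would need to add 10 pg/mL is 10 divided by the fall:

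| Start (mg/dL) | Fall to 7.0 | Slope needed (pg/mL per mg/dL) |
|---|---|---|
| 7.8 | 0.8 | 10/0.8 = 12.5 |
| 8.5 | 1.5 | 10/1.5 = 6.7 |
| 10.2 | 3.2 | 10/3.2 = 3.1 |

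The documents give no slope to compare with these.

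**Illustration, no drug effect.** Assumed curve: iPTH = 1 + (max - 1)/(1 + (cCa/8.5)^10). The maximum, minimum, set-point and slope are all assumptions. The threshold is read as 10 pg/mL, although the endpoint prints pg/dL; Section 9.3 uses pg/mL for PTH-Clamp and pg/dL for Aparathyroid.

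*Single point, max 30.* At 9.2 mg/dL: 1 + 29/(1 + 2.206) = 10.04. At 7.6 mg/dL: 1 + 29/(1 + 0.327) = 22.86. The change is +12.8 pg/mL (+128%).

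*The endpoint itself, max 30.* The baseline is held at 10.04. With peak-time cCa of 9.2, 8.8, 8.4, 8.0 and 7.6 on Days 1-5, iPTH is 10.04, 13.01, 16.36, 19.77 and 22.86. The mean is 16.41, a change of +6.4 pg/mL (+63%).

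| Peak-time cCa, Days 1-5 | Max 30 | Max 40 |
|---|---|---|
| Even fall, 9.2 to 7.6 | +6.4 | +8.6 |
| Even fall, 8.88 to 7.6 | +7.6 | +10.3 |
| 9.2, then 7.6 on Days 2-5 | +10.3 | +13.8 |

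Every path passes the 50% limb. At max 30, only the fast, sustained fall passes the 10 pg/mL limb. At max 40, the even fall from 8.88 just passes.

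These figures leave out within-day variation. Comparing a mean with daily maxima raises the change by itself. In a simulation with mean 10 pg/mL and within-person CV of 10-30%, the rise was about 1.3-4.0 pg/mL. That is a separate feature of the endpoint and is not part of the calcium effect sized here.

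**Opposite direction, same curve (max 30).** Suppose the drug raises the set-point by 10%, to 9.35. At unchanged cCa of 9.2, iPTH is 1 + 29/(1 + (9.2/9.35)^10) = 16.7, a rise of 6.6 pg/mL. If cCa also rises by 10%, to 10.12, the ratio cCa/set-point is unchanged. iPTH is then again 10.04, so the real shift shows as zero change.

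**The case against.** A reader might infer that the protocol withdraws calcium, so that PTH released by falling calcium will be credited to encaleret. The documents do not support that. Home calcium is replaced from Day -1 by supplements, diet and rescue; calcitriol is what stops without scheduled replacement. Table D is expressly a guide, and investigators may depart from it. Section 2.2 expects blood calcium to rise, which would hide a PTH effect, although Section 4.3 warns of hypocalcemia. Either direction is possible. The Day -1 and Day 1 pre-dose values also follow the last home doses, so the baseline absorbs some early change.

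A reader might also infer that a rise would be uninformative. It would not be: a PTH rise from any cause shows secretory reserve, which partly answers the Cohort 2 question. What it does not show is that encaleret caused the rise.

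It is also fair that the endpoint is tertiary with no planned test, that iPTH, cCa and ionized calcium over time are already listed endpoints, and that individual plots are permitted (Section 9.4.8). That limits the weight of the point. But permitted is not prespecified, and nothing in the plan links the two series.

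**Conclusion.** The point holds as a problem of attribution for an exploratory endpoint. The comparison has no calcium reference and no control, and it spans a change in calcitriol and calcium treatment. A rise may therefore reflect lower calcium, and a null may reflect higher calcium. Both require residual parathyroid tissue.

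The bias is possible, not demonstrated, and its size cannot be derived from the documents. On the assumed curve with maximum 30 pg/mL, calcium alone gives +12.8 pg/mL at a single point but +6.4 pg/mL on the five-day average under an even fall. There the 10 pg/mL limb is met only by a fast, sustained fall. The primary and secondary endpoint definitions do not use this iPTH change.

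**What to change.** Keep the endpoint and add the following to the SAP:

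1. **Drug-attributable contrast.** Prespecify the Day 1 change in iPTH from the mean of the -30 and -15 min draws to the mean of the 30 min, 1 h, 2 h and 4 h draws. These bracket the median t_max of 1.5 h (Section 2.2). Report the paired cCa change, because morning calcium or food may fall in that window.
2. **Individual plots.** Show each participant's iPTH against same-sample cCa, off and on drug.
3. **Interpretation.** Read the Days 1-5 average-peak change, and membership of the PTH-Clamp and Aparathyroid populations, alongside paired cCa.
4. **Adjusted model.** Treat any cCa-adjusted Days 2-5 model as supportive only. The drug itself changes cCa, so the coefficient is not the total drug effect, and off-drug points are few: about four per participant, two of them 15 minutes apart.

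Two wordings also need reconciling: the iPTH unit (pg/dL against pg/mL), and the study calcium regimen (individualised in Section 6.1.2, a fixed amount in Section 8.2).

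The cost is SAP text only, since calcium and albumin are already in the panel that gives iPTH. The limitation is that the Day 1 contrast covers a single dose over four hours and would miss a slower glandular response.

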Cohort 2: Recent PSH (<1 year after surgery) with up to 5 participants

Phase: Phase 2

Description of Sites/Facilities National Institutes of Health (NIH) Clinical Center (CC)

Enrolling Participants:

Description of Study Intervention: Encaleret will be provided as an oral film-coated tablet. Each tablet contains 54 mg of encaleret as 60 mg of encaleret sulfate (CLTX-305). Participants will receive 3 tablets twice a day (BID).

Study Duration:	Estimated time from when the study opens to enrollment until completion of data analyses is approximately 12 months.
Participant Duration:	Total duration of study participation will be 101 to 277days for each subject including between 4 and180 days between the screening visit and initiation of therapy, and 90 day follow up after discontinuation of the study drug.

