Hypoparathyroidism has a prevalence of approximately 77,000 adults in the United States with the most common cause, approximately 75%, due to complications from neck surgery (Mannstadt et al, 2017). PSH can be classified as transient (lasting <6 months) or permanent (lasting longer than 6 months). The true incidence of PSH is difficult to determine as it depends on numerous factors including the experience of the surgeon, extent of surgery, patient risk factors, and diagnosis criteria. Nevertheless, it is estimated that transient PSH affects up to 25-30% of patients undergoing total thyroidectomy, while permanent PSH occurs in up to 3% of patients (Mannstadt et al, 2018).

Hypoparathyroidism is characterized by an inappropriately low level of parathyroid hormone (PTH), hypocalcemia and hyperphosphatemia. Inadequate PTH-secretion results in lower levels of endogenous 1,25-(OH)₂ Vitamin D (decreasing calcium absorption from the gut), lower levels of calcium reabsorption in the kidney (leading to hypercalciuria), and decreased PTH-mediated bone resorption (decreasing calcium release from the bone). Symptoms of hypocalcemia include paresthesias, muscle spasms, tetany, cramps, seizures, laryngospasm, neuromuscular irritability, cognitive impairment, personality disturbances, and prolonged QT intervals.

Conventional therapy with oral calcium and calcitriol, which includes a high pill burden and is cumbersome for patients, often causes hypercalciuria, which is associated with long-term morbidity including nephrolithiasis, nephrocalcinosis and chronic kidney disease (Khan et al 2018, Li et al 2018). Managing patients with hypoparathyroidism is a challenging balance between increasing blood calcium while minimizing hypercalciuria (Gafni and Collins, 2019). Practically, this is done by targeting the lowest blood calcium that still relieves symptoms of hypocalcemia to avoid hypercalciuria.

Recombinant human PTH 1-84 (Natpara, Takeda Inc.) was approved for the treatment of hypoparathyroidism, however, the effect on hypercalciuria, renal calcifications, and renal insufficiency is unclear (Gafni et al, 2018; Rubin et al, 2016) It is also currently unavailable in the US due to a prolonged recall. Long-acting PTH preparations are being developed and show promise, but will continue to require injections, which patients are often opposed to if comparable effective orally administered treatment is available.

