8.2 Study Evaluation & Procedures

The following procedures and imaging assessments will occur according to Section 1.3 Schedule of Activities.

All participants must sign the informed Consent Form (ICF) prior to any study-related procedures. Screening must be completed within 180 days prior to admission to the NIH CC (See [Table A](#) for Schedule of Activities).

Screening Visit: The first screening visit will be conducted at the NIH CC to determine subject eligibility, document current metabolic status, and assess dietary calcium intake. Participants may complete the screening assessments as outpatients or be housed overnight at NIH CC. Participants who complete the screening visit midweek have the option to stay overnight at NIH CC during the intervening days prior to Day -1. Each subject's current treatment regimen will be assessed by NIH investigators in relation to presence/absence and control of hypocalcemia-related complaints and symptoms, and assessment of blood and urine analytes including blood and urine calcium and phosphate. NIH investigators may recommend adjustments to a subject's outpatient regimen during the screening period, in accordance with the accepted goals of achieving cCa in the low normal range, while minimizing hypercalciuria. Unscheduled outpatient laboratory assessments, if required, will be arranged through outpatient laboratories with results transmitted to and reviewed by the investigators as standard of care. Participants who complete the screening process and meet inclusion/exclusion criteria, may be scheduled for admission for the treatment period of the protocol.

Procedures/evaluations planned as part of the screening visit include:

- History and Physical examination
- Height and Weight
- Vital Signs
- Nutritionist Assessment
- Blood laboratory assessment
- Electrocardiogram (ECG)
- 24-hour urine collection (may be performed after the visit if more convenient for the patient)

- Renal Ultrasound

After completing screening assessments, any AE/SAE reported by a subject, whether or not study drug has been administered, will be recorded by the investigators. Any AE/SAE prior to dosing will be categorized as “Baseline” and any AE/SAE after dosing will be categorized as “treatment-emergent.”

Treatment Period:

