9.3 Populations for Analyses

- **Treatment Population:** All participants who received at least one dose of study drug
- **Permanent hypoparathyroidism (Cohort 1):** Participants with long-standing hypoparathyroidism who received at least one dose of study drug
- **Recent Hypoparathyroid population (Cohort 2):** Participants with recent hypoparathyroidism who received at least one dose of study drug
- **“PTH-Clamp” Population:** Participants whose iPTH did not increase more than 10 pg/mL on encaleret

- **“Aparathyroid” Population:** Participants whose absolute iPTH level was less than 10 pg/dL throughout the study
- **Hyperthyroid Population:** Participants whose TSH is less than the lower limit of normal for the assay during the treatment phase of the study
- **Normothyroid Population:** Participants whose TSH is in the normal range during the treatment phase of the study
- **Thyroid Cancer Population:** Participants with a history of thyroid cancer

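### The exploratory iPTH endpoint compares a mean of daily maxima with a mean of single baseline draws, so it shows a rise even when encaleret has no effect on PTH

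*Combined protocol and SAP*

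**What the plan says.** The Synopsis (1.1) and section 3 define the two sides of the iPTH contrast differently.

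- Baseline: "The average baseline iPTH will include all baseline iPTH levels from the screening visit, Day -1, and pre-dose on Day 1".
- On drug: "The average peak iPTH will average the peak iPTH levels on every day the patient is on encaleret (days 1 to 5".
- Decision rule: "An increase in iPTH will be considered clinically significant if there is an increase both by 50% AND by more than 10 pg/dL".

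Section 3 gives the reason for averaging: "Averaging iPTH will prevent spurious excursions from impacting outcomes".

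Table C (section 1.3) sets the number of draws, because iPTH belongs to every mineral-lab draw. Day 1 has two pre-dose and six post-dose draws, Days 2-4 have five each, and Day 5 has seven plus a 24-hour draw. Day -1 has one iPTH draw; the evening panel that day in Table A does not include PTH.

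On the age of the screening value, section 8.2 says: "Screening must be completed within 180 days prior to admission to the NIH CC". Figure 1 alone shows a 90-day window. Section 2.2 says: "PSH can be classified as transient (lasting <6 months) or permanent (lasting longer than 6 months". Cohort 2 (surgery less than 12 months ago, up to 5 participants) is included because its gland damage may be reversible.

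Section 9.3 defines the PTH-Clamp population without naming a baseline, and in a different unit: "Participants whose iPTH did not increase more than 10 pg/mL on encaleret".

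**The concern.** The maximum of several noisy readings exceeds their mean. The on-drug side takes a maximum each day and then averages the five maxima. The baseline side averages single readings. No untreated daily maximum exists to compare with, since Day -1 has one iPTH draw and the Day 1 pre-dose draws are 15 minutes apart. The averaging that section 3 relies on steadies the five maxima but leaves their upward shift in place.

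A smaller problem points the same way. If a Cohort 2 gland recovers between screening and Day -1, the old screening value pulls the baseline down, and part of that recovery is counted as a rise on encaleret.

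There is no control arm to absorb either effect. At stake is how the exploratory question of whether encaleret raises PTH is answered, particularly in participants with recent surgery, and how many participants are labelled as having a clinically significant increase.

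**Working it through.** The plan gives no expected value, variance or power for iPTH, so there is no figure of its own to reproduce.

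**Inputs from the documents.** Baseline: four samples (one screening, one Day -1, two Day 1 pre-dose). On drug: maxima over 6, 5, 5, 5 and 7 draws on Days 1-5, leaving out the Day 5 24-hour draw. Rule: a rise of 50% and of more than 10 units.

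**Assumptions.** No drug effect; lognormal noise with a within-person CV of 10-30%; independent draws unless stated; absolute cut read as 10 pg/mL unless stated.

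**Step 1: size of the peak bias.** The expected maximum of k standard normal draws is 1.163 for k = 5, 1.267 for k = 6 and 1.352 for k = 7. The mean over the five days is (1.267 + 3 × 1.163 + 1.352) / 5 = 1.22 within-person SDs. It is 1.12 if only post-dose draws count and 1.24 if the 24-hour draw is added. At CV 20% this is about 1.22 × 20% = 24%. Lognormal skew and division by a noisy baseline bring it to 27% in simulation.

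| CV | Mean apparent rise, no drug effect |
|---|---|
| 10% | +13% |
| 20% | +27% |
| 30% | +43% |

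About 98% of participants show a positive change. With a same-day correlation of 0.5 the 27% falls to about 19%: smaller, but not removed.

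**Step 2: false flags in stable participants.**

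| True iPTH (pg/mL) | CV 20% | CV 30% |
|---|---|---|
| 5 | 0% | 0% |
| 10 | 0% | 0.1% |
| 20 | 2.5% | 29% |
| 25 | 7% | 36% |

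Read literally, 10 pg/dL is 0.1 pg/mL. The absolute cut then does almost nothing, and the flag rate is about 7% (CV 20%) or 36% (CV 30%) at every level.

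**Step 3: the screening value alone.** With true level m from Day -1 onward and s at screening, the baseline is (3m + s)/4. Drift therefore contributes (m - s)/4, or (m - s)/(3m + s) as a proportion. For s = 10 and m = 20 that is 10/4 = 2.5 pg/mL, or 10/70 = 14%. The ceiling, at s = 0, is 1/3 = 33%, below the 50% rule. If the three visits rather than the four samples were weighted equally, the ceiling would be 50%, reached only at s = 0.

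**Step 4: both together.** For a 10-to-20 pg/mL recovery completed before Day -1, at CV 20%, the rule is falsely met 16% of the time with the screening value in the baseline and about 4% with it removed.

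**Step 5: a like-for-like contrast.** Take the mean of on-drug draws minus the mean of the Day -1 and Day 1 pre-dose values. The mean change is then about 0 pg/mL. At CV 30%, false flags are 0.5% or fewer up to 25 pg/mL and about 1.4% at 30 pg/mL.

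**The case against.** The strongest reply is that little depends on this contrast. The endpoint is exploratory and has no specified test. The same sections list absolute iPTH and its change from baseline over five days as a separate endpoint, section 9.4.9 allows mixed models for the repeated measures, and the Day 8-12 off-drug labs include PTH, which helps to separate recovery from a drug effect. All of this stands. A reader might infer that the peak contrast is the only evidence on whether encaleret raises PTH; the documents do not support that. What remains is that only this contrast carries the clinically significant label.

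The second reply is that the dual threshold works as a margin. That stands for participants at 5-10 pg/mL if the unit is pg/mL. It does not stand at 20-25 pg/mL if the CV is near 30%.

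The third is that gland recovery could be made to look dominant. A recovery from 5 to 25 pg/mL would meet the rule 65% of the time at CV 20%, but that is an extreme case and the figure runs from 9% to 81% over CVs of 10-30%. Screening has one-quarter weight and matters mainly in a cohort of at most five.

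Finally, the CV and the correlation are assumed. Positive same-day correlation shrinks the bias, as shown, without reversing its direction.

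**Conclusion.** The point holds as a bias in one exploratory endpoint. Its direction follows from the definition; its size rests on an assumed CV and on how far same-day draws are correlated. Peak selection is the main cause. The screening value is secondary and, as one sample in four, cannot meet the 50% rule alone. The stated justification for averaging is not met.

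A reader might go further and infer that the main result is at risk. It is not: the primary FECa analysis in the Treatment Population and its sample size do not use iPTH. PTH-Clamp membership could be affected, because its baseline is unstated, but those subgroup analyses are labelled exploratory. Severity: consider.

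**What to change.** In the Synopsis (1.1) and section 3:

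- (a) Define baseline iPTH as the mean of the Day -1 and Day 1 pre-dose values, and report screening separately. This is in line with the plan's Day -1 baseline for primary FECa and its Day 1 pre-dose baseline for 1,25-(OH)₂ vitamin D.
- (b) Apply the 50%/10-unit rule to the mean of all scheduled on-drug iPTH draws (post-dose on Day 1, all draws on Days 2-5). Keep the average daily peak as a descriptive measure, labelled as upward-biased.
- (c) State the same baseline for PTH-Clamp membership in section 9.3.
- (d) Reconcile pg/dL in the rule with pg/mL in the PTH-Clamp definition. The Aparathyroid definition also uses pg/dL and should be checked with them.

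The cost is wording only, since every sample is already scheduled. The downside is that a short post-dose PTH pulse is diluted in the mean, which matters because section 4.3 names type 2 error as a main concern; the pulse stays visible in the descriptive peak and the time course. The sponsor should also confirm that thresholds chosen for a peak are still the ones wanted for a mean. Restricting the mean to the 30-minute and 4-hour draws would be worse: section 2.2 gives a tmax range of 0.75-3 hours, so those two draws fall on either side of it.
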